10.3.2 Outcome definition and variables

Outcomes will be identified in healthcare databases, prescriptions, and registries as available in the different countries. Any diagnosis variables available in the data sources will be considered.

10.3.2.1 Malignancies

As the **primary outcome**, new malignancies will include any first haematological, solid, or skin malignancies registered in the databases in the follow-up period. Benign tumours will not be included. Incident malignancies, identified by a diagnosis listed in Table 15, will be defined as new malignancies; subsequent malignancy diagnoses will not be considered.

As **secondary outcomes**, specific types of the first malignancy diagnosis will be considered. Three groups of malignancies will be considered as separate outcomes (Table 15, objectives 6 and 7): haematological, solid, and skin cancers. Within each outcome, the frequency of specific malignancies⁵ (Table 15) (e.g., for haematological malignancies: non-Hodgkin's lymphoma, leukaemia, etc.; for solid cancers: lung, thyroid, breast, etc.) will be described.

If a patient is diagnosed with two or more malignancies during the study period, the follow-up time up to the occurrence of the first malignancy will be considered.

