Two cohorts will be constructed for the outcomes of interest (a malignancies cohort – for evaluating new malignancies as a composite outcome and for malignancies' sub-types; and a serious infections cohort – for evaluating serious infections outcomes), considering outcome-specific inclusion and exclusion criteria. In the main analysis, on-treatment definition of exposure will be considered: patients will be considered at risk while exposed to the first anifrolumab treatment (or the SOC treatment for the exposed to SLE SOC group). For the analysis of malignancy outcomes, follow-up will start after a 12-months latency period after the index date and an additional 12-months period at risk (off-drug) will be considered to capture outcomes that might occur after drug cessation.

Exposure variables

Patients exposed to anifrolumab will be defined by the initiation of anifrolumab (anatomical therapeutic chemical code L04AA51).

SLE SOC patients will be defined by the use of drugs indicated for moderate to severe SLE (in addition to antimalarials and/or low dose corticosteroids): medium to high dose corticosteroids, immunosuppressants (synthetic or biologics [except anifrolumab]), plasmapheresis or intravenous immunoglobulins.

Outcome variables

Primary outcomesCONFIDENTIAL AND PROPRIETARY16 of 130

Malignancies will be defined as the first coded diagnosis for haematological malignancies and solid tumours available in the data sources.

Serious infection will be defined as an infection leading to hospitalisation, use of intravenous antimicrobials or an infection-related death, operationalised as:

- Infections leading to hospitalisation: a) infection diagnosis as part of a hospitalisation episode or b) infection diagnosis in primary or secondary care settings up to 7 days before hospitalisation.
- Prescription/administration of intravenous antimicrobials.
- Infection-related death: recorded diagnosis of infection in primary or secondary care settings with record of death within the subsequent month.

Secondary outcomes

Specific types of malignancies: haematologic, solid and skin malignancies.

Serious infection components: infection leading to hospitalisation, infection requiring treatment with IV antimicrobials and infection-related death.

Serious infection types grouped as opportunistic serious infections, other serious infections, pneumonia (overall), fatal and non-fatal pneumonia (separately).

Exploratory outcomes

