8.4 Malignancies and knowledge gaps

Published studies have identified an increased frequency of some malignancies among patients with SLE, particularly for non-Hodgkin's lymphoma, leukaemia, and cancer of the vulva, lung, thyroid, and liver [13]. Although there is a decreased risk of other select types of cancer in patients with SLE, the overall cancer risk in SLE is slightly greater as compared with the general population [13]. Possible pathways linking SLE and malignancies include inherent immune system abnormalities, SLE medication exposures, interactions between medication and viral exposure, co-existing conditions (such as Sjögren's syndrome) and presence of "traditional" risk factors for malignancy (such as smoking, obesity and reproductive history) [10, 52, 59, 103].

Treatments that induce immune suppression may impair immune surveillance and thereby increase the risk for initiation or growth acceleration of malignancies. Furthermore, Type 1 IFNs may play a role in tumour surveillance. Therefore, while blocking type 1 IFN might be beneficial in controlling autoimmune diseases, the same pathway of suppression could potentially increase the risk of malignancies.

The impact of treatment with anifrolumab on the potential risk of malignancies is not known. In the placebo-controlled clinical trials, at any dose, malignant neoplasms (including non-melanoma skin cancers) were reported in 1.3% patients receiving anifrolumab, compared to 0.6% patients receiving placebo [92]. Malignancies excluding non-melanoma skin cancers were observed in 0.7% and 0.6% of patients receiving anifrolumab and placebo, respectively. In patients receiving anifrolumab, breast and squamous cell carcinoma were observed in more than one patient [92].

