• Most malignancies have long latency periods in the absence of immunosuppression [66]. Although immunosuppression shortens the latency period [100], current study follow-up time may be short (seven years will be the maximum duration between first enrolled patient and the end of follow-up) to identify some malignancies. Thus, the incidence may be underestimated. However, haematological malignancies are expected to be the most frequent cancer types among SLE patients [12, 13, 84]. For those, latency periods are likely to be shorter.

• Previous research suggests that biologics are associated with an increased risk of malignancies [100]. Therefore, cancer screenings (e.g., for breast or cervical cancers) and closer surveillance may be reinforced among patients exposed to biologics, namely anifrolumab [16]. If so, anifrolumab patients may have a diagnosis at an earlier time point than it would have been if it had been diagnosed by its clinical appearance. This may result in an increased risk of malignancy in anifrolumab patients. However, patients exposed to SLE SOC may also be exposed to other biologics or known carcinogenic drugs (such as cyclophosphamide) which may result in similar adherence to cancer screenings, minimising surveillance bias [41].

Capturing malignancies using claims data may be prone to misclassification because unconfirmed cases may be captured. Since no population-based cancer registry is used for France (SNDS), Germany (SHI) and Spain (SIDIAP), misclassification may occur. Additionally, in France, malignancies are only captured for patients that were hospitalised. Although virtually all patients may be hospitalised at some stage of the disease, under-detection may occur.

SLE severity and activity

• Disease severity and activity scales (e.g., Systemic Lupus Erythematosus Disease Activity Index 2000 [SLEDAI-2K score]) are frequently used in randomised controlled trials but are not routinely recorded in secondary data sources and therefore were not included. Activity could also be addressed by considering specific biomarkers (e.g., C3, C4) which are unlikely to be systematically used and available. To minimise the lack of available data, severity and activity algorithms that were previously defined [39, 56] will be used, incorporating information that is used in routine practice: scale-up of SLE treatment strategies, SLE clinical manifestations and HRU.

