Appendix 3 Exemplar code lists

Code lists will be finalised in the SAP.

Table 14 Drug classes and active substances used in SLE SOC

Drug/Procedure	ATC codes
Antimalarials	
Chloroquine	P01BA01
Hydroxychloroquine	P01BA02
Quinacrine (mepacrine)	P01AX05
Glucocorticoids	
Dexamethasone	H02AB02
Methylprednisolone	H02AB04
Prednisolone	H02AB06
Prednisone	H02AB07
Triamcinolone	H02AB08
Immunosuppressive agents	
Biologic immunosuppressants	
Anifrolumab (drug of interest)	L04AA51
Belimumab	L04AA26
Rituximab (including reference product and biosimilars)	L01FA01
Synthetic immunosuppressants	
Anakinra	L04AC03
Apremilast	L04AA32
Azathioprine	L04AX01
Baricitinib	L04AA37
Cyclophosphamide	L01AA01
Cyclosporine	L04AD01
Leflunomide	L04AA13
Methotrexate	L04AX03
Mycophenolic acid/sodium ¹	L04AA06
Sirolimus	L04AA10
Tacrolimus	L04AD02
Thalidomide	L04AX02
Tofacitinib	L04AA29
Voclosporin	L04AD03
Immunoglobulins	
Immunoglobulin G	J06BA02
Plasmapheresis	
Plasmapheresis (procedure)	B05AX03

	ICD-10 codes
	C00-C96
	D00-D09
Malignancies	
-	
All haematological (malignant	C81-C96
neoplasms of lymphoid,	
haematopoietic and related tissue)	
Leukaemia	C91-95
Lymphoma	C81-88, C96
Hodgkin's lymphoma	C81
Non-Hodgkin's lymphoma	C82-86, C96
	C90
plasma cell neoplasms	
All	C00-13, C15-16, C18-23, C25, C32-34, C45, C50-
	54, C56, C60-62, C64-65, C67, C70-73
Bladder	C67
Breast	C50
Cervix uteri	C53
Endometrium	C54.1
Oesophagus	C15
Gastric	C16
Liver	C22
Lung	C33-34
Oropharynx	C09-10
Larynx	C32
Ovary	C56
Prostate	C61
Renal	C64-65
Thyroid	C73
Vagina	C52
Vulva	C51
All (melanoma and other malignant neoplasms of skin)	C43-C44
	neoplasms of lymphoid, haematopoietic and related tissue) Leukaemia Lymphoma Hodgkin's lymphoma Non-Hodgkin's lymphoma Multiple myeloma and malignant plasma cell neoplasms All Bladder Breast Cervix uteri Endometrium Oesophagus Gastric Liver Lung Oropharynx Larynx Ovary Prostate Renal Thyroid Vagina Vulva All (melanoma and other malignant

Abbreviations: ICD-10, international statistical classification of diseases tenth revision.

	ICD-10 codes
All serious infections (composite)	A00-B99, D73.3, E06.0, E32.1, G00-G02, G04.2, G05-G07, H00.0, H44.0,
[81]	H60.0, H60.1, H60.2, H60.3, H66, H67, H70, I30.1, I40.0, J00-J22, J34.0,
	J36, J38.3, J39.0, J39.1, J44.0, J85, J86, K04.4, K04.6, K04.7, K10.2,
	K11.3, K12.2, K14.0, K57.0, K57.2, K57.4, K57.8, K61, K63.0, K65.0,
	K65.9, L00-L04, L05.0, L08, N10-N12, N13.6, N15.1, N15.9, N30.0,

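### Table 15 places in-situ neoplasms (D00-D09) in the primary malignancy list but in no sub-type, and no composite or pooled estimate is planned without them or without non-melanoma skin cancer

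*Protocol*

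**What the plan says.** The protocol describes the primary malignancy outcome in three places.

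- **Section 10.3.2.1, prose:** "new malignancies will include any first haematological, solid, or skin malignancies registered in the databases in the follow-up period. Benign tumours will not be included". Later malignancies are ignored, and person-time stops at the first one.
- **Section 10.3.2.1, operational rule:** "Incident malignancies, identified by a diagnosis listed in Table 15, will be defined as new malignancies".
- **Abstract:** "Malignancies will be defined as the first coded diagnosis for haematological malignancies and solid tumours available in the data sources". Skin is not named here.

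Table 15 (Appendix 3) opens with C00-C96 and D00-D09. It then gives haematological (C81-C96), a selected list of solid-tumour C codes, and skin. The single skin row, whose label begins "All (melanoma and other malignant neoplasms of skin", carries C43-C44 with no further split. Appendix 3 adds: "Code lists will be finalised in the SAP".

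Three other sections bear on this:

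- Section 8.4, after giving 1.3% vs 0.6% for all malignant neoplasms, reports: "Malignancies excluding non-melanoma skin cancers were observed in 0.7% and 0.6% of patients receiving anifrolumab and placebo, respectively".
- Section 10.9 accepts that "cancer screenings (e.g., for breast or cervical cancers) and closer surveillance may be reinforced among patients exposed to biologics, namely anifrolumab".
- Section 10.7.1.7 plans sensitivity analyses on latency, comparator type and the meta-analysis model. Section 10.7.1.6 limits meta-analysis to the primary objectives.

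**The concern.** The prose names three groups, while the code list that implements it adds a fourth block, in-situ neoplasms, that belongs to none of them. Two programmers could each follow the protocol and produce different primary outcomes.

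In-situ lesions of the breast and cervix are found largely by screening, so they are the events most exposed to the surveillance difference raised in Section 10.9. Section 10.3.3.1 says screening data may not be available in every source, so adjustment cannot be relied on and the outcome definition has to carry more of the control. Because only the first malignancy counts, an in-situ lesion also removes a later invasive cancer from view.

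The skin grouping raises a related problem. The trial results look different with and without non-melanoma skin cancer, but this study plans no composite that allows the same comparison.

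**Working it through.** **1. Code coverage.** D00-D09 is in Table 15's opening codes and in none of C81-C96, the solid list or C43-C44. The label of that opening row is not readable in the text I worked from, so treating it as the composite row is an inference. No other row could hold D00-D09. Some C codes in the range (for example C14, C17, C24) are also in no sub-type, but those still fit the prose as solid malignancies.

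**2. What the planned estimates contain.**

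| Estimate | Counts D00-D09 | Counts C44 | Pooled |
|---|---|---|---|
| Primary composite HR | yes, by Table 15 | yes | yes |
| Haematological HR | no | no | no |
| Solid HR | no | no | no |
| Skin HR | no | yes, with C43 | no |

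Table 2 also ends follow-up for the sub-type objectives at the first malignancy. Read literally, an in-situ lesion therefore censors those analyses even though it is not an event in them.

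**3. The trial figures (Section 8.4).** With non-melanoma skin cancer: 1.3/0.6 = 2.17. Without: 0.7/0.6 = 1.17. Excess with: 1.3 − 0.6 = 0.7 points. Part due to non-melanoma skin cancer alone: (1.3 − 0.7) − (0.6 − 0.6) = 0.6 points, and 0.6/0.7 = 86%. The inputs have one decimal. Taking the two placebo figures as equal, rounding alone allows (1.25 − 0.75)/(1.25 − 0.55) = 71% up to 100%.

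**4. The plan's own sample size.** I simulated the Section 10.5.2 design with 40,000 runs: Table 13 country shares, log HR normal with mean ln 1.5 = 0.405 and SD 0.132, 6.31 per 1000 person-years, 1:3, 5 years, DerSimonian-Laird pooling, two-sided 5%. Power at 3,195 exposed is 79.2-79.6% against the stated 80%. At 3,000 it is 78.2% (Table 10: 0.780) and at 3,500 it is 81.2% (0.814). The figure reproduces.

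**5. Dilution.** Let f be the share of comparator events that are in-situ or C44. The documents do not give f, so 10-50% is assumed. With a true HR of 1.5 on the rest and 1.0 on f, the composite HR is 1 + 0.5(1 − f). The total rate is held at 6.31; if the share is excluded, the rate becomes 6.31(1 − f) and the HR stays 1.5.

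| f | Composite HR | Power, included | Power, excluded |
|---|---|---|---|
| 10% | 1.45 | 74% | 77% |
| 20% | 1.40 | 67% | 75% |
| 30% | 1.35 | 59% | 72% |
| 50% | 1.25 | 41% | 64% |

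**6. Excess detection.** With HR 1.0 on the rest and an assumed detection ratio of 2 on f, the composite HR is 1 + f. That is 1.20, 1.30 and 1.50 at f = 20%, 30% and 50%, with a 31%, 50% and 79% chance of a significant pooled result. These chances include the between-source SD of 0.132, which itself adds to them: at a composite HR of 1.05 the simulation gives 11%, against 6% without heterogeneity.

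**7. In-situ lesions alone.** Assume r = 1 to 4 in-situ events per 1000 person-years on top of 6.31.

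- True invasive HR 1.5, no in-situ effect: (1.5 × 6.31 + r)/(6.31 + r) = 1.43 to 1.31.
- True invasive HR 1.0, in-situ detection raised 1.5-fold: (6.31 + 1.5r)/(6.31 + r) = 1.07 to 1.19.

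**The case against.** The best defence is that Section 10.3.2.1 itself makes Table 15 the operative list, so prose and table together describe a deliberately broad composite. The lists are labelled exemplar and will be finalised in the SAP. The plan also has safeguards:

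- a 12-month latency period with a 24-month variant;
- a comparison with patients on SOC biologics, who may be screened similarly;
- screening covariates where a source holds good data;
- sub-type HRs that count neither D00-D09 nor C44.

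Much of this stands, and it rules out several stronger readings that a reader might infer:

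- *That the sentence on benign tumours excludes in-situ lesions.* It does not; in-situ neoplasms are not benign. The conflict is with the three named groups.
- *That a non-melanoma excess could not appear anywhere.* It would appear in the skin HR, mixed only with melanoma.
- *That the protocol expects more screening on anifrolumab.* Section 10.9 says it may occur, and adds that comparators may be screened similarly.
- *That the trials establish a non-melanoma signal.* Section 8.4 gives small percentages without counts or intervals.

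The defence does not resolve the inconsistency. The grouping is fixed in protocol text, and it disagrees with the list that the same paragraph invokes. Latency removes lesions found soon after initiation, not those found at later screening rounds. The biologics comparison changes the comparator, not the mix of events. The estimates free of both groups are single-country only.

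France, with 74.56% of the planned sample (Table 13), sees only hospital-coded malignancies, while Denmark uses a cancer registry. That may shrink the effect overall, but it also means the composite may capture different lesions by country.

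**Conclusion.** The inconsistency is real and cheap to correct. Under Table 15 as it stands, in-situ lesions are primary events and end follow-up, and no planned composite or pooled estimate removes them or C44. They can raise the composite HR through unequal detection, or pull a true effect on invasive cancer toward 1.

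The size is not established. Every figure in steps 5 to 7 of the working rests on an assumed event share or rate and, where used, an assumed detection ratio. Section 10.5.2 does not say whether 6.31 includes in-situ lesions. The conclusion also rests on reading the opening row of Table 15 as the composite. This is an improvement that should be made, not a flaw that invalidates the study.

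**What to change.** 1. Reconcile Section 10.3.2.1, the abstract and Table 15: remove D00-D09 from the primary composite, name the same groups in all three places, and tabulate in-situ neoplasms separately by arm.
2. Split the skin sub-type in Table 15 into melanoma (C43) and non-melanoma (C44).
3. Add to Section 10.7.1.7 a sensitivity analysis of the primary composite excluding C44, by country and in the meta-analysis. Keeping C44 in the primary composite preserves comparability with the trials' overall figure, and the sensitivity analysis matches their second figure.

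The cost is a code-list edit, one extra run of the existing Cox and meta-analysis models, and somewhat fewer composite events. If the removed events carry no treatment effect, step 5 of the working shows that exclusion gives more power than inclusion despite the lower count.

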10.3.2.2 Serious infections

Serious infections are generally defined as those that result in death, are life-threatening; require inpatient hospitalisation or prolongation of existing hospitalisation; require treatment with IV antimicrobials (e.g., antibiotics, antifungals, antivirals); result in persistent or significant disability/incapacity; or are, based upon appropriate medical judgement, important medical events that may not be immediately life-threatening or result in death or hospitalisation but may jeopardise the patient or may require intervention to prevent one of the other outcomes listed above [22, 27]. It may not be possible to identify all serious infections using this definition since it is not possible to assess some of its components from the secondary data sources e.g., if a particular infection prolonged an existing hospitalisation or led to disability.

Thus, for current study, the **primary outcome** serious infection will be defined as infections leading to hospitalisation, use of IV antimicrobials, or death. It will be defined as either of:

- Infections leading to hospitalisation:
 - Infection diagnosis as part of a hospitalisation episode (including primary and secondary diagnoses) (Table 16) [8, 78]
 - Infection diagnosis in primary or secondary care settings up to 7 days before hospitalisation (Table 16) [9, 79]

⁵The specific malignancies were defined based on the previously described increased or decreased risk among SLE patients when compared to the general population [12, 13, 84].

- Infections requiring treatment with IV antimicrobials:
 - Prescription/administration of IV antimicrobials (Table 19) [46, 51]
- Infection-related death:
 - Recorded diagnosis of infection (Table 16) in primary or secondary care settings with record of death within the subsequent 30 days [30].

Detailed operational definitions to identify the availability of serious infections data in different data sources as disease coding systems used will be defined in the SAP.

The first serious infection after index date will be included. Date of each serious infection episode will be the date of infection leading to hospitalisation, use of IV antimicrobials or death, whichever occurs first. The frequency of each serious infection component – infection leading to hospitalisation, requiring treatment with IV antimicrobials and infection-related deaths – will be described as a **secondary** objective (secondary objective 8) and comparative analyses on each component will be conducted as sensitivity analysis, where possible (Section 10.7.1.7).

As **secondary outcomes**, opportunistic serious infections, other serious infections, pneumonia (overall, fatal and non-fatal) will be analysed separately (objectives 9 and $10)^6$. Additionally, the proportion of serious infections due to COVID-19 infection will be described for patients exposed and unexposed to anifrolumab.

The definition of opportunistic infections may be challenging. To define opportunistic infections detailed clinical information is often needed and, at some level almost all agents could be considered opportunistic in that they are typically more likely to occur, or present more severely in immunosuppressed patients [99]. Therefore, classifying infections as opportunistic using secondary data is challenging. In recognition of this challenge, efforts have been made by a consensus committee (which included infectious disease, public health, and pulmonary physicians with subject matter expertise in mycobacterial, fungal, viral, bacterial or parasitic infections, as well as rheumatology physicians) to harmonize a list of infections that could be considered as opportunistic for use in clinical trials and observational studies involving biologics and other disease modifying antirheumatic drugs. The consensus list of infections was based on a systematic review of several observational studies, clinical trials, case series, and expert opinion by the committee [99].

In this study, opportunistic infections are defined based on the list of infections provided by the consensus committee with two considerations: all infections that could be mapped to ICD-10 codes

⁶Opportunistic infections are reported to be frequent among patients with autoimmune diseases. *Herpes zoster* has the highest incidence rate (IR), although frequently not considered a serious infection [47]. This is in line with results from anifrolumab RCTs that also describe *herpes zoster* as a frequent infection, together with respiratory tract infections [29]. Other classification of serious infections (by pathogen: bacterial, viral, fungal, etc) was considered but discounted, because the probability of pathogen misclassification is high in the selected data sources. Furthermore, in the available healthcare coded registries in about one third of infections the infections pathogen was not identified [76].

with certainty (Table 17) have been included; and infections (e.g., shigella) which require invasive or disseminated presentations in order to be considered opportunistic, for which there are no specific ICD-10 codes for invasive disease have been excluded.

Within all serious infections, a subset of other clinically relevant serious infections will be analysed, including respiratory tract infections (including pneumonia), sepsis, COVID-19, urinary tract infections and infections during pregnancy (Table 18).

Pneumonia will be defined regardless of the microbiologic aetiology (Table 18). Pneumonia will be analysed as a composite outcome of all identified cases and separately for fatal and non-fatal cases. Fatal pneumonia cases will be defined according to the above proposed definition of infection-related death, i.e., cases with record of death in the 30 days after the diagnosis date. All cases that do not meet this definition will be considered non-fatal.

All infections leading to hospitalisation (the first and recurrent episodes) will be considered as **exploratory outcomes**. A recurrent episode of infection will be defined as an infection leading to hospitalisation (code list available in Table 16) occurring more than 30 days after the hospital discharge date of the previous infection leading to hospitalisation.

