• Identification opportunistic infections may require detailed clinical information – that may not be available in secondary data [99]. Despite this challenge, in a diagnostic validation study which aimed to evaluate the reliability of identifying opportunistic infections (tuberculosis, listeriosis, aspergillosis, histoplasmosis, cryptococcosis, pneumocystis carinii, systemic candidiasis and cytomegalovirus) using ICD-10 codes in an administrative claims data, the positive predictive value (PPV) varied between 20% for systemic candidiasis to 100% for cryptococcosis. The PPV for all the opportunistic outcomes investigated, excluding systemic candidiasis was greater than 66%. As a composite outcome, excluding candidiasis, the PPV was 76% [80].

• There are varying definitions of opportunistic infections. While it may be challenging to identify one formal definition, a comprehensive list of potential opportunistic infections, which represents a systematic review-informed consensus opinion by infectious disease and rheumatology experts, relevant in rheumatology has been ratified by a consensus committee [99]. The consensus committee acknowledge that while this list is neither complete nor absolutely "correct", the presence of the infections in this list may be indicative of an altered host immunity playing an aetiological role in the setting of biologic therapy. The limitation in the use of this list from the consensus committee for this study is that not all conditions on the list have ICD codes (hepatitis B reactivation, invasive Shigella infection, invasive Campylobacter infection and BK virus causing polyomavirus-associated nephropathy). Therefore, these infections will not be captured. Additionally, some unspecific codes (e.g., pneumonia with no defined pathogen, other sepsis) will not be defined as opportunistic. This will increase the specificity of the opportunistic serious infections definition but may result in decreased sensitivity of the outcome.

• Date of death will be identified by linking data to administrative records or mortality registries available in the study countries. The added sensitivity of including death registries for patients with a prior infection diagnosis (regardless of cause of death) may come at the expense of decreased specificity by considering deaths that might occur 30 days after an infection diagnosis but are not related with the infection episode.

Outcome assessment: malignancies

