	Zygomycosis	Gastrointestinal mucormycosis	B46.2
		Disseminated mucormycosis	B46.4
		Eumycetoma	B47.0
	Mycetoma	Actinomycetoma	B47.1
		Mycetoma, unspecified	B47.9
	Othersment	Rhinosporidiosis	B48.1
	Other mycoses, not elsewhere classified	Allescheriasis	B48.2
	(including	Geotrichosis	B48.3
	Penicillium	Penicillosis	B48.4
	marneffei and	Pneumocystosis	B48.5
	Pneumocystosis)	Opportunistic mycoses	B48.7
	Unspecified	Unspecified mycosis	B49
	Leishmaniasis	Visceral leishmaniasis	B55.0
		Acute Chagas disease with heart involvement	B57.0
Parasitic	Chagas disease	Acute Chagas disease without heart involvement	B57.1
		Chagas disease (chronic) with heart involvement	B57.2

Group	Subgroup Clinical Code Description		ICD-10
		Chagas disease (chronic) with digestive system involvement	B57.3
		Chagas disease (chronic) with nervous system involvement	B57.4
		Chagas disease (chronic) with other organ involvement	B57.5
		Toxoplasma oculopathy	B58.0
		Toxoplasma hepatitis	B58.1
		Toxoplasma meningoencephalitis	B58.2
To	Toxoplasmosis	Pulmonary toxoplasmosis	B58.3
		Toxoplasmosis with other organ involvement	B58.8
		Toxoplasmosis, unspecified	B58.9
	Strangedaidiasis	Intestinal strongyloidiasis	B78.0
	Strongyloidiasis	Disseminated strongyloidiasis	B78.7
	Cryptosporidiosis	Cryptosporidiosis	A07.2
		Other specified protozoal intestinal diseases	A07.8
	Microsporidiosis	Other specified protozoal diseases	B60.8

Abbreviations: ICD-10, international statistical classification of diseases tenth revision; CMV, cytomegalovirus infection

Subgroup	Clinical Code Description	ICD-10
	Influenza with pneumonia, virus not identified	J11.0
	Viral pneumonia, not elsewhere classified	J12
Pneumonia ^a	Pneumonia due to Streptococcus pneumoniae	J13
Pheumoma	Pneumonia due to Haemophilus influenzae	J14
	Bacterial pneumonia, not elsewhere classified	J15
	Pneumonia in diseases classified elsewhere	J17
Acute bronchitis and	Acute bronchitis	J20
bronchiolitis	Acute bronchiolitis	J21
	Acute nasopharyngitis [common cold]	J00
	Acute sinusitis	J01
	Acute pharyngitis	J02
Acute upper	Acute tonsillitis	J03
respiratory infections	Acute laryngitis and tracheitis	J04
	Acute obstructive laryngitis [croup] and epiglottitis	J05
	Acute upper respiratory infections of multiple and unspecified sites	J06
	Coronavirus infection, unspecified site	B34.2
	Coronavirus as the cause of diseases classified to other chapters	B97.2
	Pneumonia due to SARS-associated coronavirus	J12.81

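### The exemplar pneumonia list in Table 18 omits J18, J16 and J10.0, although Section 10.3.2.2 cites that table for a definition covering pneumonia of any cause

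*Protocol*

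**What the plan says.** Section 10.3.2.2 of the protocol sets the definition and names the table that puts it into practice: "Pneumonia will be defined regardless of the microbiologic aetiology (Table 18". It then fixes the outcomes that depend on it: "Pneumonia will be analysed as a composite outcome of all identified cases and separately for fatal and non-fatal cases". These are secondary outcomes under objectives 9 and 10. The same section uses Table 18 for the group of other clinically relevant serious infections, which includes pneumonia.

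In Table 18 (Appendix 3) the pneumonia block opens with J11.0, "Influenza with pneumonia, virus not identified", continues through J12, J13, J14 and J15, and closes with J17, "Pneumonia in diseases classified elsewhere". The next row is acute bronchitis, J20.

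Table 16, the list for the serious infection composite, contains the run "I30.1, I40.0, J00-J22, J34.0".

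Two other places bear on the point. Section 10.9 says that "some unspecific codes (e.g., pneumonia with no defined pathogen, other sepsis) will not be defined as opportunistic". Footnote 6 in Section 10.3.2.2, explaining why infections are not grouped by pathogen, reports that "in about one third of infections the infections pathogen was not identified". Appendix 3 opens with the statement: "Code lists will be finalised in the SAP".

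**The concern.** A definition that disregards the organism should include the code used when no organism is recorded. Table 18 leaves that code out, along with two others, while the text points to Table 18 as the definition. A programmer who follows the table and one who follows the sentence would count different events.

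Pneumonia is not a marginal outcome here. Section 8.3 reports it as the most frequent non-opportunistic serious infection in the long-term phase III data, in both arms, and as the leading cause of fatal infection. An incomplete list lowers the incidence estimates of objective 9 directly and removes events from the comparisons of objective 10, which are run only if the sample size allows. Section 10.9 adds that results with fewer than five cases may not be reportable in every database. That limit would bind first for fatal pneumonia.

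**Working it through.** The plan gives no pneumonia event count, rate or power figure, so there is no stated number to reproduce. The check is a comparison of code lists, followed by an illustration of size.

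**Step 1: codes.** Section 10.3 adopts the 2019 WHO ICD-10. The meanings of the three absent codes are taken from that classification.

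| Code | Table 18, pneumonia rows | Table 16 (J00-J22) |
|---|---|---|
| J10.0 influenza pneumonia, virus identified | absent | covered |
| J11.0 | listed | covered |
| J12, J13, J14, J15 | listed | covered |
| J16 pneumonia, other infectious organisms | absent | covered |
| J17 | listed | covered |
| J18 pneumonia, organism unspecified | absent | covered |

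A J18 admission is therefore a serious infection under Table 16 but not a pneumonia under Table 18.

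**Step 2: is the restriction deliberate?** Nothing in the protocol says so, and three points suggest otherwise.

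- Section 10.9 recognises pneumonia without a defined pathogen as a code and removes it from the opportunistic group only. Its companion example there, other sepsis (A41), does appear in Table 18. The pneumonia code appears in neither Table 17 nor Table 18, so it belongs to no named sub-type.
- Footnote 6 rejects classification by pathogen because misclassification is likely and pathogens often go unidentified. Leaving out the organism-unspecified code runs against that reasoning.
- J11.0 is included without its virus-identified counterpart J10.0, and no reason is given.

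**Step 3: size.** Let u be the share of pneumonia cases carrying an omitted code, the same in both groups. Table 2 ends follow-up for objectives 9 and 10 at the first serious infection, so a J18 case would stop contributing person-time without counting as a pneumonia event. Hence

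- incidence rate as listed = (1 − u) × full incidence rate.

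With event counts d1 and d0 in the two groups, SE(log HR) ≈ √(1/d1 + 1/d0). Multiplying both counts by (1 − u) gives

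- SE factor = 1/√(1 − u).

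| Assumed u | Incidence multiplied by | SE(log HR) multiplied by |
|---|---|---|
| 20% | 0.80 | 1/√0.80 = 1.12 |
| 33% (one third) | 0.67 | 1/√0.667 = 1.22 |
| 50% | 0.50 | 1/√0.50 = 1.41 |
| 70% | 0.30 | 1/√0.30 = 1.83 |

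Every value of u is an assumption. The protocol gives none for pneumonia.

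**The case against.** The strongest reply is that the list is provisional. Table 18 is headed as an exemplar, Appendix 3 leaves finalisation to the SAP, and Section 10.3.2.2 leaves operational definitions of serious infection there too. On that view the sentence in the text governs, and it is right. This lowers the weight of the point but does not remove it. The sentence cites the table as its content, and the table as written gives a different answer. Four data sources would start from it, and two of them (Germany and Spain) are analysed by the data provider.

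A second reply is that the listed rows are not tied to single organisms. That is correct: only J13 and J14 name one, while J11.0, J12, J15 and J17 are broader. The list is incomplete; it would be wrong to call it the reverse of the definition.

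A third concerns extraction. Another row of Table 18 has lost its code in the available text, so a lost pneumonia row cannot be fully excluded. But the three missing codes belong at three separate positions in an otherwise unbroken block, which makes that explanation unlikely.

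A reader might also infer from footnote 6 that at least a third of pneumonias would be missed. The protocol does not support this. The figure concerns all infections, and an unidentified pathogen does not mean a J18 code: J11.0 explicitly keeps cases without an identified virus, and J12 or J15 may hold others.

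**Conclusion.** The mismatch between Section 10.3.2.2 and Table 18 stands, with J18 as the omission that matters most and J16 and J10.0 as secondary. If the list is carried forward, pneumonia overall, fatal and non-fatal, and the other-serious-infections group built on Table 18, will be under-captured. Incidence falls by the missed share. Precision falls by 1/√(1 − u), which is 1.12 to 1.83 over an assumed 20% to 70%. Those factors rest on equal missing in both groups and on shares that the protocol does not supply, so it cannot be said how severe the undercount would be.

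Two stronger readings should be set aside. The primary serious infection result is not affected, because Table 16 covers all three codes. Nor does the protocol show that the hazard ratio would be biased: that would require organism testing or coding to differ between the groups, and nothing in the text establishes this. The finding is an inconsistency in secondary outcomes that should be corrected before data extraction.

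**What to change.** Correct the pneumonia rows of Table 18 to J10.0, J11.0 and J12-J18, keeping the COVID-19 pneumonia codes. Carry that single list into the final SAP code lists for overall, fatal and non-fatal pneumonia and for the other-serious-infections group.

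Also state whether organism-specific pulmonary codes now placed in Table 17, such as A48.1 (Legionnaires disease), B25.0 (cytomegaloviral pneumonitis) and B48.5 (pneumocystosis), count as pneumonia. A definition that ignores aetiology leaves that open, and adding J10.0, J16 and J18 does not settle it. If a narrower outcome is in fact intended, say so, give the reason, and reword the sentence in Section 10.3.2.2.

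The cost is a code-list edit and one clarifying sentence. No design, sample size or primary analysis changes. It is best done before data extraction, planned to start on 31 May 2025.
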